5. STUDY CONDUCT

5.1 Restrictions during the study

There are no specific dietary or activity restrictions other than those typical for this patient population.

Patients should not donate blood or bone marrow at any time during the study period.

Restrictions regarding concomitant medications are described in Section 5.6

5.2 Subject enrolment

The Investigator will:

1. Obtain signed informed consent (ICF) from the potential subject or their guardian/legal representative before any study specific procedures are performed. If ICF is not signed by the subject himself/herself, the subject should sign the ICF after his/her capability recovers.
2. Assign potential subject a unique enrolment number, beginning with 'E#'.
3. Determine subject eligibility. See Sections 4.1 and 4.2

If a subject withdraws from participation in the study, then his/her enrolment code cannot be reused.

5.2.1 Procedures for randomisation (Not applicable)

5.3 Procedures for handling subjects incorrectly enrolled

Subjects who fail to meet the inclusion/exclusion criteria should not, under any circumstances, be enrolled. There can be no exceptions to this rule.

If a patient does not meet the selection criteria but is enrolled in error, a discussion should occur between the Study Physician and the Investigator regarding whether to continue or discontinue the patient from study medication. Consistent with Intent-To-Treat (ITT) principles, all enrolled patients should continue to be followed in the study (ie, attend protocol visits) and, unless treatment would be harmful, patients should continue to receive study medication.

In situations where an agreement cannot be reached, the patient should have their study medication stopped but will continue with study assessments. The Study Physician is to ensure all such decisions are appropriately documented.

5.4 Blinding and procedures for unblinding the study (Not applicable)

5.5 Treatments

5.5.1 Identity of investigational product(s)

Investigational product	Dosage form and strength	Manufacturer
Ticagrelor 90 mg	Plain, round, yellow, film-coated tablet, 90 mg	AstraZeneca

5.5.2 Doses and treatment regimens

Ticagrelor 180mg loading dose taken orally, followed by 90mg bd

5.5.3 Additional study drug (Not applicable)

5.5.4 Labelling

Labels will be prepared in accordance with Good Manufacturing Practice (GMP) and local regulatory guidelines. The labels will fulfil GMP Annex 13 requirements for labelling. Label text will be translated into local language.

The label will include the following information:

- Name of sponsor (AstraZeneca)
- Study drug dosage form, route of administration, and quantity of dosage units
- Storage conditions
- Study code
- Enrolment code
- Space for Subject Number to be written
- Directions for use
- Space for visit number to be written
- The name of the Investigator, where applicable (this may be pre-printed or to be added on the label when the investigational product / study drug is dispensed)

- The period of use eg, expiry date
- Keep out of reach of children
- For clinical trial use only

5.5.5 Storage

All study drugs should be kept in a secure place under appropriate storage conditions. The investigational product label on the pack specifies the appropriate storage.

5.6 Concomitant and post-study treatment(s)

In addition to the assigned study medication, all patients will take concomitant ASA, at a planned dose of 100 mg once daily, from enrolment through the end of the treatment period. If a patient develops an indication for higher dose ASA during the treatment period (e.g. acute coronary syndrome or percutaneous coronary intervention), higher dosing is allowed for the duration of that indication, after which the dose of ASA should be reduced to 100 mg once daily.

Other medication, which is considered necessary for the subject's safety and well being, may be given at the discretion of the investigator and recorded in the appropriate sections of the electronic Case Report Form (eCRF).

Investigators are reminded of the following potential drug-drug interactions.

5.6.1 Digoxin and other p-glycoprotein interactions

Ticagrelor modestly increases digoxin levels. Therefore digoxin levels should be monitored closely following initiation or discontinuation of ticagrelor. Other p-glycoprotein substrates may be expected to have similar changes in pharmacokinetics. Additional details can be found in the package insert for ticagrelor.

5.6.2 CYP450 interactions

5.6.2.1 CYP3A inhibitors

Strong inhibitors of CYP3A enzyme (eg, ketoconazole, itraconazole, voriconazole, telithromycin, clarithromycin [but not erythromycin or azithromycin], nefazadone, ritonavir, saquinavir, nelfinavir, indinavir, atazanavir, or over 1 litre daily of grapefruit juice) should not be co-administered with ticagrelor, as plasma levels of ticagrelor would be substantially increased.

5.6.2.2 CYP3A substrates or inducers

Concomitant therapy with simvastatin or lovastatin at doses higher than 40 mg daily is not permitted since administration with ticagrelor will result in higher serum concentrations and may put patients receiving more than 40 mg per day of simvastatin or lovastatin at increased risk of statin-related adverse effects. There are no restrictions to other statin therapies (ie,

doses of simvastatin or lovastatin \leq 40 mg daily or any dose of any other statin is permitted). Investigators are advised to check lipid levels and adjust statin dosages per local practice.

Co-administration of ticagrelor with strong inducers of CYP3A also should be avoided (eg, rifampin/rifampicin, rifabutin, phenytoin, carbamazepine, phenobarbital).

5.6.3 Oral anticoagulants

Concomitant treatment with oral anticoagulants (ie, vitamin K antagonists, direct thrombin inhibitors, factor X inhibitors) is not recommended during the study. The investigator should carefully consider potential risks and benefits. Irrespective if study drug is stopped or not, the patient should remain in the study for evaluation.

5.6.4 Parental anticoagulants

Short-term treatment (ie, up to 7 days) with approved parenteral anticoagulants (eg, unfractionated heparin (UFH), low-molecular-weight heparin (LMWH), bivalirudin, fondaparinux) is allowed. However, long-term treatment with LMWH or fondaparinux in outpatients (at venous thrombosis treatment or atrial fibrillation doses) in combination with study medication is not allowed. Concomitant treatment with venous thrombosis prophylaxis doses is allowed.

5.6.5 ADP receptor antagonists

Concomitant treatment with any other ADP receptor antagonists is not allowed in the study.

5.6.6 GPIIb/IIIa receptor antagonists

Short-term treatment (ie, up to 7 days) with GPIIb/IIIa antagonists is allowed during the study.

5.6.7 Dipyridamole and cilostazol

Concomitant treatment with dipyridamole or cilostazol is not permitted in the study.

5.6.8 Fibrinolytic treatment

If a patient is to be treated with fibrinolytic therapy, study medication should be stopped and restarted no earlier than 24 hours after completion of the fibrinolytic therapy and when the risk of bleeding is deemed low in the judgment of the investigator.

5.6.9 Non-steroidal anti-inflammatory drugs (NSAIDs)

Chronic treatment with non selective NSAID treatment or prostacyclin (PGI₂) is not permitted. Short term treatment with NSAID or PGI₂ up to 7 days is allowed.

5.7 Treatment compliance

The administration of all study drugs (including investigational products) should be recorded in the appropriate sections of the eCRF.

Patients will be asked to return all unused study medications and empty packages to the clinic at each visit. The patient's compliance will be assessed by the investigator and recorded in the eCRF. A pill count should be done at a patient level and recorded in the eCRF and a dispensing log by the study site personnel.

5.7.1 Accountability

The study drug provided for this study will be used only as directed in the study protocol.

The study site personnel will account for all study drugs dispensed to and returned from the subject.

Study site personnel will account for all study drugs received at the site, unused study drugs and for appropriate destruction. Certificates of delivery, destruction and return should be signed.

5.8 Discontinuation of investigational product

Subjects may be discontinued from investigational product (IP) in the following situations:

Adverse Event as judged by the investigator and/or AZ

Severe non-compliance to study protocol as judged by the investigator and/or AZ

Subjects should be discontinued from investigational product (IP) in the following situations:

Subject decision. The subject is at any time free to discontinue treatment, without prejudice to further treatment

Incorrectly enrolled patient in whom the inclusion/exclusion criteria violation would put the patient at undue risk (see Section 5.3)

Pregnancy

5.8.1 Procedures for discontinuation of a subject from investigational product

A subject that decides to discontinue investigational product will always be asked about the reason(s) and the presence of any adverse events. Adverse events will be followed up (See Sections 6.4.3 and 6.4.4); and all study drugs should be returned by the subject.

5.8.2 Temporary discontinuation from study medication

Surgery or procedures associated with major haemorrhage: It is recommended that cardiac surgery and major non-cardiac surgery that in the opinion of the investigator poses a risk for clinically major bleeding not be performed until at least 5 days after stopping study medication to avoid excessive bleeding. After surgery, study medications should be restarted when the risk of bleeding is deemed low in the judgment of the investigator.

Major bleeding: Study medication must be stopped immediately in case of a bleeding deemed to be clinically significant in the judgment of the investigator (eg, a significant fall in haemoglobin, need for transfusion, haemodynamically significant, or in a critical location such as intracranial, intraspinal, intraocular, or pericardial), but may be reinstated when the risk of bleeding is deemed low in the judgment of the Investigator and if not contraindicated. The study medication administration need not be stopped in case of a minor bleeding. All bleedings should be treated and followed up according to local clinical practice. Major bleeding events should be managed according to need with general support and blood.

Study medication should be restarted at the investigator's discretion to minimise the risk of thrombotic complications

Dyspnea: Evaluation of a patient who develops dyspnea should start with an assessment of timing relative to initiation of study drug, severity, and the presence of any signs or symptoms suggestive of cardiopulmonary disease. In patients with signs and symptoms suggestive of another cause of dyspnea (eg, heart failure exacerbation, chronic obstructive pulmonary disease flare), evaluation and treatment for those conditions should occur per local practice standards. Importantly, study drug should be continued in these patients without interruption.

Also, in patients in whom the dyspnea begins soon after starting study drug and not associated with any signs or symptoms suggestive of significant cardiopulmonary disease, patients should **continue study drug without interruption** as the dyspnea typically resolves spontaneously while on treatment. The patient should be re-evaluated after several days. It is important to note that a drug holiday and subsequent rechallenge often results in recurrence of dyspnea.

In patients with dyspnea likely due to study drug that proves intolerable, concomitant medications should be reviewed and, **when possible**, moderate CYP3A4 inhibitors (eg, diltiazem) changed to an alternative that is not a CYP3A4 inhibitor or discontinued.

5.8.3 Permanent premature discontinuation from study medication

Patients permanently discontinuing study medication should be given conventional therapy, if applicable. This medication(s) will be open label and obtained locally. All patients should always be asked to continue the regular visits as described below. **It is essential to collect as much data as possible for all patients throughout the study. Complete withdrawal from the study (withdrawal of consent) has a direct impact on the potential validity of all study data and should be avoided wherever possible.**

If the patient prematurely permanently discontinues study medication, there could be several different options for their continuation in the study as described below.

5.8.3.1 The patient agrees to undergo the premature treatment discontinuation visit and then continue in-person study visits

The patient agrees to undergo the Premature Treatment Discontinuation Visit (PTDV) and then continue in-person study visits every 3 months until 12 months after enrolment. This is the preferred option and patients who discontinue study medication will always be asked if they agree to this approach.

5.8.3.2 The patient unwilling to continue in-person study visits but agrees to undergo modified follow-up

If the patient agrees, the PTDV should be done. Subsequent visits through Visit 6 will be done as regular telephone contacts or by other means to ascertain whether any clinical endpoints or AEs have occurred and to inventory concomitant medications. Such a patient has not withdrawn his/her consent or withdrawn from the study.

5.8.3.3 The patient refuses any form of follow-up

If the patient refuses any form of follow-up, he/she officially withdraws from the study and withdraws consent. This approach should be avoided if possible.

5.9 Withdrawal from study

Subjects are at any time free to withdraw from study (investigational product and assessments), without prejudice to further treatment (withdrawal of consent). Such subjects will always be asked about the reason(s). If possible, they will be seen and assessed by an investigator; final visits should be 1 week after the discontinuation (See Table 2). Adverse events will be followed up by the investigator for as long as medically indicated, but without further recording in the eCRF); and all study drugs should be returned by the subject.

The Investigator should always ask the patient to allow contact 12 months after enrolment for a final follow-up to ascertain AEs even if participation in other visits is not agreed. At a minimum, permission to ascertain vital status should be obtained if at all possible. This agreement should be noted and signed by both the Investigator and the patient on the Informed consent form, as well as entered in the medical records. The reason for discontinuation and the date of discontinuation from the study must be documented in the eCRF.

Withdrawn subjects will not be replaced.

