6.3 Efficacy

Suspected clinical efficacy endpoints will be collected in the eCRF. These events will be identified using standard questioning of the patient at each visit, or by information that the investigator may receive as part of standard medical practice. Safety endpoint events will be identified similarly.

For each suspected endpoint, the investigator will collect relevant additional source information where required, determine whether a safety or efficacy endpoint has occurred, and record their finding on the eCRF.

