6.3.1 CV death

All deaths reported post-enrolment will be recorded and classified by the investigator as CV or non-CV.

6.3.2 MI

MI is diagnosed on the basis of elevation of myocardial necrosis biomarkers typical of acute MI with **at least 1 of the following:**

1. Recurrent cardiac ischaemic symptoms ≥ 20 minutes at rest
2. Development of new pathological Q waves on the ECG
3. New or presumed new ECG changes indicative of ischaemia in 2 or more contiguous leads (ST-segment elevation, ST-segment depression or T-wave inversion)

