6.4.3 Recording of adverse events

Time period for collection of adverse events

AE/SAEs will be recorded from the time of signature of informed consent throughout the treatment period, including the follow-up period, to last contact.

Follow-up of unresolved adverse events

Any AEs that are unresolved at the subject's last AE assessment in the study are followed up by the investigator for as long as medically indicated, but without further recording in the eCRF. AstraZeneca retains the right to request additional information for any subject with ongoing AE(s)/SAE(s) at the end of the study, if judged necessary.

Variables

The following variables will be collect for each AE;

- AE (verbatim)
- The date when the AE started and stopped
- Whether the AE is serious or not
- Investigator causality rating against the Investigational Product (yes or no)
- Action taken with regard to investigational product
- Outcome.

In addition, the following variables will be collected for SAEs:

- Date AE met criteria for serious AE
- Date Investigator became aware of serious AE
- AE is serious due to
- Date of hospitalisation
- Date of discharge
- Probable cause of death
- Date of death
- Autopsy performed
- Causality assessment in relation to Study procedure(s)

- Causality assessment in relation to other medication

Description of AE

The following definitions for intensity rating are:

- mild (awareness of sign or symptom, but easily tolerated)
- moderate (discomfort sufficient to cause interference with normal activities)
- severe (incapacitating, with inability to perform normal activities)

It is important to distinguish between serious and severe AEs. Severity is a measure of intensity whereas seriousness is defined by the criteria in Section 6.4.2. An AE of severe intensity need not necessarily be considered serious. For example, nausea that persists for several hours may be considered severe nausea, but not a SAE. On the other hand, a stroke that results in only a limited degree of disability may be considered a mild stroke but would be a SAE.

Causality collection

The Investigator will assess causal relationship between Investigational Product and each AE, and answer 'yes' or 'no' to the question 'Do you consider that there is a reasonable possibility that the event may have been caused by the investigational product?'

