6.4.4 Reporting of serious adverse events

All SAEs have to be reported, whether or not considered causally related to the investigational product, or to the study procedure(s). All SAEs will be recorded in the eCRF.

If any SAE occurs in the course of the study, then investigators or other site personnel inform appropriate AstraZeneca representatives immediately, or **no later than 24 hours** of when he or she becomes aware of it.

The designated AstraZeneca representative works with the investigator to ensure that all the necessary information is provided to the AstraZeneca Patient Safety data entry site **on the day** of initial receipt for fatal and life threatening events **and within five calendar days** of initial receipt for all other SAEs.

For fatal or life-threatening adverse events where important or relevant information is missing, active follow-up is undertaken immediately. Investigators or other site personnel inform AstraZeneca representatives of any follow-up information on a previously reported SAE immediately, or **no later than 24 hours** of when he or she becomes aware of it.

Once the Investigators or other site personnel indicate an AE is serious in the WBDC system, an automated email alert is sent to the designated AstraZeneca representative.

If the WBDC system is not available, then the Investigator or other study site personnel reports a SAE to the appropriate AstraZeneca representative by telephone.

The AstraZeneca representative will advise the Investigator/study site personnel how to proceed.

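### Section 5.9 drops the limit that 6.4.3 puts on its no-recording clause, so sites may differ on whether an MI or stroke found at the month-12 contact of a withdrawn patient is entered in the eCRF

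*Protocol*

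**What the plan says.** Section 5.9 covers patients who leave the study altogether, meaning both study drug and assessments. On adverse events it says: "Adverse events will be followed up by the investigator for as long as medically indicated, but without further recording in the eCRF". The following paragraph says: "The Investigator should always ask the patient to allow contact 12 months after enrolment for a final follow-up to ascertain AEs", even when the patient declines other visits, and this agreement is to be signed by both sides. The only eCRF entry that 5.9 itself requires is this: "The reason for discontinuation and the date of discontinuation from the study must be documented in the eCRF".

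The general recording rules read differently:

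- Section 6.4.3: "AE/SAEs will be recorded from the time of signature of informed consent throughout the treatment period, including the follow-up period, to last contact".
- Section 6.4.3, on events that are unresolved at the patient's "last AE assessment in the study are followed up by the investigator for as long as medically indicated, but without further recording in the eCRF".
- Section 6.4.4: "All SAEs will be recorded in the eCRF".

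Endpoints also have rules of their own. Section 6.3: "Suspected clinical efficacy endpoints will be collected in the eCRF". Section 6.3.1: "All deaths reported post-enrolment will be recorded and classified by the investigator as CV or non-CV".

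**The concern.** The clause in 5.9 is worded almost exactly like the one in 6.4.3 but lacks its limit. In 6.4.3 it closes the record on an event that has already been entered and is still running at the last assessment. In 5.9, as written, it applies to every adverse event after withdrawal, including new ones. The same section then sets up a contact to look for such events and does not say where the result goes.

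This matters most for MI and stroke. Both are adverse events, normally serious, and both are components of the primary efficacy composite. If a site takes 5.9 at its word, an event that the patient agreed to report and the investigator found could stay out of the database. Another site with the same finding could enter it under 6.3 or 6.4.4. In a single-arm study of about 100 patients whose purpose is to describe a one-year incidence, that handling should not be left to each site.

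**Working it through.** **The plan's own figure.** Section 12.3 gives a precision of ±4.3% for a 5% rate in 100 patients: 1.96 × √(0.05 × 0.95 / 100) = 0.0427, which agrees. The point here does not depend on it.

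**The rules side by side, for a patient who withdraws and agrees to the month-12 contact.**

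| Finding at month 12 | 5.9 read literally | Other sections | Place in the planned analysis |
|---|---|---|---|
| New MI or stroke | Not entered, as an AE | Entered (6.3, 6.4.3, 6.4.4) | Eligible for the composite (12.2.1) |
| Death | Not entered, as an AE | Recorded and classified (6.3.1) | Eligible if CV |
| Bleed or other SAE later than 7 days after last dose, or after study termination | Not entered | Entered (6.4.3, 6.4.4) | Outside the safety analysis (12.2.2) |
| Bleed or other SAE inside those limits, reported late | Not entered | Entered | Inside the safety analysis |
| AE already recorded and still unresolved at the last assessment | No further entry | No further entry (6.4.3) | Unchanged |

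Only the last row is free of conflict.

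**Why MI, stroke and CV death count.** The synopsis bases the primary efficacy analysis on every patient who took at least one dose, whether or not the patient stayed in the study. Section 12.2.1 censors event-free patients at study closure or at last available information, if earlier. Neither place cuts follow-up at withdrawal of consent.

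**How many events.** The protocol gives no withdrawal rate. Assume w = 2 to 15 withdrawals in 100 patients. For the one-year risk p, use the ticagrelor K-M rates for the composite in Table 1: 9.8% (overall), 13.0% (Asian) and 15.7% (Taiwan). Assume withdrawn patients carry the same risk as the others, at a constant hazard.

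- All withdraw at the start (upper bound): expected events = w × p.
- All withdraw at mid-year: expected events = w × (1 − √(1 − p)). The remaining-year risks are 5.0%, 6.7% and 8.2%.

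| w | p = 9.8%: start / mid-year | p = 13.0%: start / mid-year | p = 15.7%: start / mid-year |
|---|---|---|---|
| 2 | 0.20 / 0.10 | 0.26 / 0.13 | 0.31 / 0.16 |
| 5 | 0.49 / 0.25 | 0.65 / 0.34 | 0.79 / 0.41 |
| 10 | 0.98 / 0.50 | 1.30 / 0.67 | 1.57 / 0.82 |
| 15 | 1.47 / 0.75 | 1.95 / 1.01 | 2.36 / 1.23 |

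The chance of at least one such event runs from 1 − 0.902 = 0.10 (two mid-year withdrawals at 9.8%) to 1 − 0.843^15 = 0.92 (fifteen at the start at 15.7%). These are events that occur after withdrawal. Fewer would be found, because not every patient will allow the contact.

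**Effect on the estimate.** One event in 100 patients is 1 percentage point. The K-M estimate falls by about that much per lost event only if withdrawn patients stay in the risk set to month 12, that is, if event-free contacts extend follow-up while events go unrecorded. If neither result is entered, the patient is censored at the last information available, and the estimate is biased only to the extent that withdrawn patients differ in risk from those who remain.

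**The case against.** The strongest reply is that 5.9 merely repeats 6.4.3. Section 5.8.1 has a sentence built the same way for patients who stop study drug, and there it points to 6.4.3 and 6.4.4 for the follow-up of adverse events. On that reading the 5.9 clause means only events unresolved at the last assessment, and the sections agree. The month-12 contact also has a purpose only if its results are recorded, and 5.8.3 stresses collecting as much data as possible. This may well be the intent. But the limit is not in the text of 5.9, and a site handling a withdrawal will turn to 5.9.

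A reader might go further and infer that an MI, stroke or bleed found at the contact cannot reach the analysis. The documents do not support that:

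- Suspected endpoints go into the eCRF under 6.3, including those the investigator learns of through ordinary care, and 6.3.1 covers all deaths after enrolment. Section 5.9 closes neither route. It does not confirm them either: 5.8.3.2 describes modified follow-up as looking for clinical endpoints or AEs, while 5.9 names AEs only.
- The final visit is less exposed than the month-12 contact. Section 5.9 refers to Table 2, and the premature treatment discontinuation column there schedules both AEs and major CV events, SAEs and bleeding.
- Withdrawal includes stopping study drug. Section 12.2.2 censors safety data 7 days after the last dose and includes patients who withdraw consent only up to study termination. A bleed or SAE beyond those limits is out of the safety analysis whether or not it is entered.
- The duty to tell the sponsor of an SAE within 24 hours (6.4.4) does not depend on the automated eCRF alert.

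The scope is also narrow. Patients who only stop study drug stay in follow-up under 5.8.3.1 or 5.8.3.2.

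**Conclusion.** The conflict is real and should be corrected. Read literally, 5.9 contradicts 6.4.3 and 6.4.4 on what is recorded after withdrawal, and it leaves open whether an MI or stroke found at the agreed month-12 contact is entered, although the primary efficacy analysis is meant to count it. Different sites could reasonably do different things.

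The size is small: probably zero to about two events in 100 patients, under the assumptions of 2 to 15 withdrawals and Table 1 risk, with not all events found. The numbers would be lower if the hazard is concentrated soon after the index event, and higher if withdrawn patients are at greater risk. The conclusion also takes the End of Treatment Visit in 12.2.1 to be the month-12 visit; Table 2 does not use that name.

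Two stronger conclusions are tempting and do not follow. One is that the events are certain to be lost. The other is that the incidence can only be lowered, by a point per event; that needs event-free contacts to extend follow-up while events are left out, and the protocol does not say so. For bleeds and other SAEs the concern is limited to those inside the 12.2.2 limits but reported late.

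**What to change.** Change 5.9 in two places, and carry the change into the eCRF instructions:

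1. Restore the 6.4.3 limit, so that only adverse events already recorded and still unresolved at the last assessment are followed without further eCRF entry.
2. State that any death, MI, stroke or SAE found at the final visit or at the agreed month-12 contact is entered in the eCRF with its onset date, and that CV deaths, MIs and strokes among these count under 12.2.1. All deaths are entered so that they can be classified under 6.3.1.

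The safety limits in 12.2.2 need no change for this purpose; onset dates let the existing rule be applied to bleeds and SAEs. The cost is a sentence or two of text and a little extra data entry for a few patients. The eCRF already has to hold adverse events and endpoints, and the contact and the signed agreement are already planned.
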